N923	Ovulation bleeding				
N924	Excessive bleeding in the premenopausal period				
N930	Postcoital and contact bleeding				
N938	Other specified abnormal uterine and vaginal bleeding				
N939	Abnormal uterine and vaginal bleeding, unspecified				
N950	Postmenopausal bleeding				
O208	Other haemorrhage in early pregnancy				
O209	Haemorrhage in early pregnancy, unspecified				

ICD-10	ICD10Name				
O441	Placenta praevia with haemorrhage				
O469	Antepartum haemorrhage, unspecified				
O679	Intrapartum haemorrhage, unspecified				
O695	Labour and delivery complicated by vascular lesion of cord				
0717	Obstetric haematoma of pelvis				
O720	Third-stage haemorrhage				
0721	Other immediate postpartum haemorrhage				
0722	Delayed and secondary postpartum haemorrhage				
O901	Disruption of perineal obstetric wound				
O902	Haematoma of obstetric wound				
P021	Fetus and newborn affected by other forms of placental separation and haemorrhage				
P100	Subdural haemorrhage due to birth injury				
P101	Cerebral haemorrhage due to birth injury				
P102	Intraventricular haemorrhage due to birth injury				
P103	Subarachnoid haemorrhage due to birth injury				
P109	Unspecified intracranial laceration and haemorrhage due to birth injury				
P120	Cephalhaematoma due to birth injury				
P269	Unspecified pulmonary haemorrhage originating in the perinatal period				
P510	Massive umbilical haemorrhage of newborn				
P519	Umbilical haemorrhage of newborn, unspecified				
P523	Unspecified intraventricular (nontraumatic) haemorrhage of fetus and newborn				
P524	Intracerebral (nontraumatic) haemorrhage of fetus and newborn				
P528	Other intracranial (nontraumatic) haemorrhages of fetus and newborn				
P529	Intracranial (nontraumatic) haemorrhage of fetus and newborn, unspecified				
P540	Neonatal haematemesis				
P542	Neonatal rectal haemorrhage				
P543	Other neonatal gastrointestinal haemorrhage				
P544	Neonatal adrenal haemorrhage				
P545	Neonatal cutaneous haemorrhage				
P546	Neonatal vaginal haemorrhage				
P549	Neonatal haemorrhage, unspecified				
P580	Neonatal jaundice due to bruising				
P581	Neonatal jaundice due to bleeding				
R040	Epistaxis				
R041	Haemorrhage from throat				
R042	Haemoptysis				
R048	Haemorrhage from other sites in respiratory passages				
R049	Haemorrhage from respiratory passages, unspecified				
R18	Ascites				
R195	Other faecal abnormalities				
R233	Spontaneous ecchymoses				
R31	Unspecified haematuria				

Page 44 of 51

ICD-10	ICD10Name				
R571	Hypovolaemic shock				
R58	Haemorrhage, not elsewhere classified				
S000	Superficial injury of scalp				
S001	Contusion of eyelid and periocular area				
S002	Other superficial injuries of eyelid and periocular area				
S003	Superficial injury of nose				
S004	Superficial injury of ear				
S005	Superficial injury of lip and oral cavity				
S007	Multiple superficial injuries of head				
S008	Superficial injury of other parts of head				
S013	Open wound of ear				
S019	Open wound of head, part unspecified				
S050	Injury of conjunctiva and corneal abrasion without mention of foreign body				
S051	Contusion of eyeball and orbital tissues				
S063	Focal brain injury				
S064	Epidural haemorrhage				
S065	Traumatic subdural haemorrhage				
S066	Traumatic subarachnoid haemorrhage				
S068	Other intracranial injuries				
S098	Other specified injuries of head				
S100	Contusion of throat				
S101	Other and unspecified superficial injuries of throat				
S141	Other and unspecified injuries of cervical spinal cord				
S241	Other and unspecified injuries of thoracic spinal cord				
S271	Traumatic haemothorax				
S272	Traumatic haemopneumothorax				
S278	Injury of other specified intrathoracic organs				
S279	Injury of unspecified intrathoracic organ				
S301	Contusion of abdominal wall				
S302	Contusion of external genital organs				
S341	Other injury of lumbar spinal cord				
S361	Injury of liver or gallbladder				
S368	Injury of other intra-abdominal organs				
S369	Injury of unspecified intra-abdominal organ				
S370	Injury of kidney				
S378	Injury of other pelvic organs				
S390	Injury of muscle and tendon of abdomen, lower back and pelvis				
S400	Contusion of shoulder and upper arm				
S408	Other superficial injuries of shoulder and upper arm				
S500	Contusion of elbow				
S501	Contusion of other and unspecified parts of forearm				
S600	Contusion of finger(s) without damage to nail				
-					

ICD-10	ICD10Name		
S601	Contusion of finger(s) with damage to nail		
S701	Contusion of thigh		
S800	Contusion of knee		
S801	Contusion of other and unspecified parts of lower leg		
S901	Contusion of toe(s) without damage to nail		
S902	Contusion of toe(s) with damage to nail		
T009	Multiple superficial injuries, unspecified		
T060	Injuries of brain and cranial nerves with injuries of nerves and spinal cord at neck level		
T090	Superficial injury of trunk, level unspecified		
T093	Injury of spinal cord, level unspecified		
T140	Superficial injury of unspecified body region		
T144	Injury of nerve(s) of unspecified body region		
T145	Injury of blood vessel(s) of unspecified body region		
T146	Injury of muscles and tendons of unspecified body region		
T794	Traumatic shock		
T810	Haemorrhage and haematoma complicating a procedure, not elsewhere classified		
T811	Shock during or resulting from a procedure, not elsewhere classified		
T876	Other and unspecified complications of amputation stump		
T905	Sequelae of intracranial injury		
	Subgaleal hemorrhage		
	Intracranial hemorrhage		

10.3.5. other codes

Subgroups	ICD10 code	Standard disease code	Note
Hypertension			Refer to 10.3.1
Liver dysfunction			Refer to 10.3.1
Renal impairment			Refer to 10.3.1
	A162		Include only tubercular hemoptysis
	A165		Include only tubercular hemothorax
	B303		
	D500		
	D62		
Bleeding	D66		Include only hemophiliac bleeding
history	D683		Include only hemorrhagic disorder due to circulating anticoagulants
	D698		
	D699		
	E078		Include only thyroid bleeding
	E274		Include only adrenal bleeding

PFIZER CONFIDENTIAL

Page 46 of 51

Subgroups	ICD10 code	Standard disease code	Note
	G361		
			Include only hematomyelia, spinal subdural
	G951		hemorrhage, hematorrhachis, spinal epidural
			hemorrhage and spontaneous Cervical Epidural
			Hematoma
	G968		Include only spinal subarachnoid hemorrhage
	H052		Include only orbital fat hemorrhage
	H113		
	H168		Include only Hemorrhagic keratitis
	H208		Include only hemorrhagic iritis
	H210 H313		
	H350		Include only hemorrhagic retinitis and juvenile recurrent
			vitreoretinal hemorrhage
	H356		
	H357		Include only hemorrhagic retinal pigment epithelial detachment
	H405		Include only hemorrhagic glaucoma
	H431		
	H448		Include only intraocular hemorrhage
	H470		Include only optic disc hemorrhage and optic nerve
			sheath hemorrhage
	H603		Include only otitis externa hemorrhagica
	H669		Include only hemorrhagic otitis media
	H738		Include only eardrum bleeding
	H922		
	1213		Include only Atrial thrombus as current complication following acute myocardial infarction
	1230		
	1312		
	1600		
	1601		
	1602		
	1603		
	1604		
	1605		
	1606		
	1607		
	1608		
	1609		
	1610		
	1611		
	1613		
	1614		
	1615		
	1616		
	l618		

PFIZER CONFIDENTIAL

Page 47 of 51

Subgroups	ICD10 code	Standard disease code	Note
	1619		
	1620		
	1621		
	1629		
	1638		Include only hemorrhagic cerebral infarction
	1690		· · ·
	l691		
	1780		
	1788		
	1850		
	1864		Include only gastric variceal bleeding
	J041		Include only hemorrhagic tracheitis
	J339		Include only bleeding polyp
	J90		Include only hemorrhagic pleural effusion
	J942		
	J950		Include only bleeding from a tracheostomy site
	K049		Include only hemorrhage in the pulp
	K068		Include only gingival hemorrhage
	K121		Include only hemorrhagic stomatitis
	K137		Include only oral hemorrhage
	K148		Include only tongue root submucosal bleeding
	K226		
	K228		Include only esophageal hemorrhage
	K250		
	K252		
	K254		
	K256		
	K260		Exclude acute gastroduodenal mucosal lesion
	K262		
	K264		
	K266		
	K284		
	K290		
	K571		Include only Duodenal diverticulum bleeding
	K573		Include only bleeding from Sigmoid diverticulum,
			Transverse colon diverticulum, Descending colon
			diverticulum, Ascending colon diverticulum and Large
	KGOE		intestine diverticulum
	K625		Include only Hemerrheidel external hemerrheide
	K649		Include only Hemorrhoidal external hemorrhoids, Hemorrhoids and Hemorrhoidal internal hemorrhoids
	K661		
	K001 K762		
	K762		Include only benatorrhagia
	K859		Include only hepatorrhagia Include only acute hemorrhagic necrotizing pancreatitis
	K059 K920		monute only acute nemormagic neorolizing partited lills
	K920 K921		
	17971		

PFIZER CONFIDENTIAL

Page 48 of 51

Subgroups	ICD10 code	Standard disease code	Note
	K922		
	L508		Include only hemorrhagic urticaria
	M2506		
	M2509		
	N029		
	N288		Include only perirenal bleeding, nephrorrhagia and idiopathic hematuria
	N300		Include only acute hemorrhagic cystitis
	N304		Include only radiation-induced hemorrhagic cystitis
	N309		Include only hemorrhagic cystitis
	N328		Include only bladder hemorrhage
	N368		Include only urethremorrhagia
	N421		
	N488		Include only penile hemorrhage
	N501		Include only Scrotal hemorrhage and Spermatic cord hematoma
	N645		Include only thelorrhagia
	N830		Include only follicular hemorrhage and hemorrhagic
			follicular cyst
	N831		Exclude luteal cyst
	N836		
	N837		
	N838		Include only ovarian hemorrhage
	N898		Include only vaginal hematoma
	N908		Include only vulval hemorrhage
	N921		
	N922		
	N923 N924		
	N924 N930		
	N938		
	N939		
	N950		
	0717		
	O901		
	O902		
	R040		
	R041		
	R042		
	R048		
	R049		
	R18		Include only hemorrhagic ascites
	R195		Include only fecal occult blood
	R233		
	R31		
	R571		Include only hemorrhagic shock
	R58		

Page 49 of 51

Subgroups	ICD10 code	Standard disease code	Note
	S000		Include only ecchymoma, hematoma and hemorrhage
	S001		Include only hematoma and hemorrhage
	S002		Include only hematoma
	S003		Include only hematoma and hemorrhage
	S004		Include only hematoma and hemorrhage
	S005		Include only hematoma and hemorrhage
	S007		Include only hematoma and hemorrhage
	S008		Include only hematoma
	S013		Include only hemorrhage
	S050		Include only Corneal hematoma
	S051		Include only traumatic vitreous hemorrhage and traumatic hyphema
	S063		Include only hematoma and hemorrhage
	S064		,
	S065		
	S066		
	S068		Include only hematoma, hemorrhage
	S098		Include only hemorrhage
	S100		Include only hematoma
	S101		*
	S141		Include only hematoma
	S241		Include only hematoma
	S271		
	S272		
	S278		Include only hematoma
	S279		Include only hematoma
	S301		Include only hematoma
	S302		Include only hematoma
	S341		Include only hematoma
	S361		Include only hematoma
	S368		Include only hemorrhage
	S369		Include only hematoma
	S370		Include only hematoma
	S378		Include only hemorrhage
	S390		Include only hematoma
	S400		Include only hematoma
	S408		Include only hematoma
	S500		Include only hematoma
	S501		Include only hematoma
	S600		Include only hematoma
	S601		Include only hematoma
	S701		Include only hematoma
	S800		Include only hematoma
	S801		Include only hematoma
	S902		Include only hematoma
	T009		Include only hematoma and hemorrage
	T060		Include only spinal subarachnoid hemorrhage

Page 50 of 51

Subgroups	ICD10 code	Standard disease code	Note
	T090		Including only hematoma
	T093		Including only hematoma
	T140		Including only hematoma
	T144		Include only traumatic hematomyelia
	T145		Include only traumatic arterial hematoma
	T146		Include only Intramuscular hematoma
	T794		Include only traumatic hemorrhagic shock
	T810		Include only hematoma and hemorrage
	T811		Include only hemorragic shock
	T876		Include only hematoma
	T905		Include only sequelae after
Hemorrhage stroke			Refer to 10.3.1
	E244		
	E52		Include only Alcoholic pellagra
	F100		
	G312		
	G405		Include only alcoholic epilepsy
	G621		
	G701		Include only alcoholic neuropathy
Alcohol abuse	G721		
	H470		Include only alcoholic optic neuropathy
	I426		
	K292		
	K70		
	K852		
	K860		
	T519		
Antiplatelet drug			Refer to 5.4
NSAIDs			Refer to 5.4
	F54		Include only psychogenic gastric ulcer
	K221		
	K227		Include only Barrett's esophagus
	K25		
Peptic ulcer	K26		
	K27		
	K28		
	K51		
	K626		
	K633		
Active cancer			Refer to 10.3.1
Diabetes mellitus	_		Refer to 10.3.1
CCI			

Page 51 of 51

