5.2. SAFETY ENDPOINTS

5.2.1. Primary safety endpoint and primary analyses

Primary safety endpoint is incidence of major bleeding, which is defined as any bleeding requiring hospitalization.

1. Incidence of Major bleeding (per 1,000 person-year)

PFIZER CONFIDENTIAL

Page 11 of 51

- Survival curves of major bleeding-free patients (Kaplan-Meier curves) will be drawn for apixaban and warfarin cohorts. Difference in the two curves will be evaluated by a Logrank test.
- Risk of major bleeding in each cohort will be compared between balanced warfarin and balanced apixaban cohorts by using Cox proportional hazard analysis. Hazard ratio with 95% confident intervals will be calculated.

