7.1.2.1. Calculation of propensity score

Propensity scores will be estimated by calendar year of index date based on multivariable logistic regression analyses that incorporate potential predictors of therapy as independent variables in the regression and cohort status (prescription of warfarin or apixaban) as the outcome. Consecutive calendar years of index dates may be collapsed to build logistic regression model with robustness. The following covariates will be included in the logistic regression:

- age on index date
- age at NVAF diagnosis
- gender

PFIZER CONFIDENTIAL

- CHADS₂ score in baseline
- CHA₂DS₂-VASc score in baseline
- heart failure diagnosis in baseline
- coronary heart disease diagnosis in baseline
- peripheral arterial disorder diagnosis in baseline
- myocardial infarction diagnosis in baseline
- hyperthyroidism or thyrotoxicosis in baseline
- TIA diagnosis in baseline
- stroke or SE diagnosis in baseline
- renal dysfunction diagnosis in baseline
- liver dysfunction diagnosis in baseline
- bleeding diagnosis in baseline
- hypertension diagnosis in baseline
- diabetes mellitus diagnosis in baseline
- treated with antiplatelet drug in baseline
- treated with NSAIDs in baseline
- treated with gastric secretion inhibitor in baseline
- treated with statin-based drug in baseline
- treated with anti-hypertensives in baseline
- treated with anti-arrhythmics in baseline
- treated with beta-blockers in baseline
- treated with heparins in baseline
- cardioversion in baseline

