10.3.3. Stroke related medical history

Disease	ICD10 code	Standard disease code	Note
Homorrhago	160		
Hemorrhage stroke	l61		
SUDKE	162		Exclude non-traumatic extradural haemorrhage
	163		
		3489032	
		4371003	
		4379014	
Ischemic stroke		3448002	
		3448028	
		3489029	
		3489035	
		4379006	
	H340		
	G450		
TIA	G451		
	G458		
	G459		
	1740		Include only abdominal aortic embolism
	1741		Include only aortic embolism
	1742		Include only acute arterial occlusive disease of
	1/42		arteries of upper extremities
	1743		Include only femoral arterial occlusion and acute
Systemic			arterial occlusive disease of arteries of lower
embolism			extremities
	1744		
	1745		Include only iliac artery embolism
	1748		Include only hepatic artery embolism
	1749		Include only thromboembolism, embolic infarction, aortic embolism
	1748		Include only subclavian artery stenosis

10.3.4. bleeding

Procedure for definition of "bleeding"

Step 1. To extract the following group A or group B from MDV data base.

Group A: ICD-10 name includes "出血 (bleeding)" or "血腫 (ecchymoma)"

Group B: Disease name includes "出血 (bleeding)" or "血腫 (ecchymoma)"

Step 2. To select disease names considered to be relevant to side effect of OAC individually from disease names excluded in Step 1.

Step 3. To exclude disease names which are not considered to be relevant to side effect of OAC from the disease names included in Step 1.

ICD-10	ICD10Name
A162	Tuberculosis of lung, without mention of bacteriological or histological confirmation
A165	Tuberculous pleurisy, without mention of bacteriological or histological confirmation

ICD-10	ICD10Name				
B303	Acute epidemic haemorrhagic conjunctivitis (enteroviral)				
D500	Iron deficiency anaemia secondary to blood loss (chronic)				
D62	Acute posthaemorrhagic anaemia				
D66	Hereditary factor VIII deficiency				
D683	Haemorrhagic disorder due to circulating anticoagulants				
D698	Other specified haemorrhagic conditions				
D699	Haemorrhagic condition, unspecified				
E078	Other specified disorders of thyroid				
E274	Other and unspecified adrenocortical insufficiency				
G361	Acute and subacute haemorrhagic leukoencephalitis [Hurst]				
G951	Vascular myelopathies				
G968	Other specified disorders of central nervous system				
H052	Exophthalmic conditions				
H113	Conjunctival haemorrhage				
H168	Other keratitis				
H208	Other iridocyclitis				
H210	Hyphaema				
H313	Choroidal haemorrhage and rupture				

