H350	Background retinopathy and retinal vascular changes				
H356	Retinal haemorrhage				
H357	Separation of retinal layers				
H405	Glaucoma secondary to other eye disorders				
H431	Vitreous haemorrhage				
H448	Other disorders of globe				
H470	Disorders of optic nerve, not elsewhere classified				
H603	Other infective otitis externa				
H669	Otitis media, unspecified				
H738	Other specified disorders of tympanic membrane				
H922	Otorrhagia				
1213	Acute transmural myocardial infarction of unspecified site				
1230	Haemopericardium as current complication following acute myocardial infarction				
1312	Haemopericardium, not elsewhere classified				
1600	Subarachnoid haemorrhage from carotid siphon and bifurcation				
1601	Subarachnoid haemorrhage from middle cerebral artery				
1602	Subarachnoid haemorrhage from anterior communicating artery				
1603	Subarachnoid haemorrhage from posterior communicating artery				
1604	Subarachnoid haemorrhage from basilar artery				
1605	Subarachnoid haemorrhage from vertebral artery				
1606	Subarachnoid haemorrhage from other intracranial arteries				
1607	Subarachnoid haemorrhage from intracranial artery, unspecified				
1608	Other subarachnoid haemorrhage				
1609	Subarachnoid haemorrhage, unspecified				

ICD-10	ICD10Name				
l610	Intracerebral haemorrhage in hemisphere, subcortical				
l611	Intracerebral haemorrhage in hemisphere, cortical				
l613	Intracerebral haemorrhage in brain stem				
l614	Intracerebral haemorrhage in cerebellum				
1615	Intracerebral haemorrhage, intraventricular				
l616	Intracerebral haemorrhage, multiple localized				
l618	Other intracerebral haemorrhage				
1619	Intracerebral haemorrhage, unspecified				
1620	Subdural haemorrhage (acute)(nontraumatic)				
l621	Nontraumatic extradural haemorrhage				
1629	Intracranial haemorrhage (nontraumatic), unspecified				
1638	Other cerebral infarction				
1690	Sequelae of subarachnoid haemorrhage				
1691	Sequelae of intracerebral haemorrhage				
1780	Hereditary haemorrhagic telangiectasia				
1788	Other diseases of capillaries				
1841	Internal hemorrhoid with other complications				
1844	External hemorrhoid with other complications				
1848	Unspecified hemorrhoid with other complications				
1850	Oesophageal varices with bleeding				
1864	Gastric varices				
J041	Acute tracheitis				
J339	Nasal polyp, unspecified				
J90	Pleural effusion, not elsewhere classified				
J942	Haemothorax				
J950	Tracheostomy malfunction				

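### As printed, both SAP bleeding lists admit code I213 under a non-bleeding name: atrial thrombus in 10.3.5, acute myocardial infarction in 10.3.4

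*SAP*

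**What the plan says.** SAP 10.3.4 builds the definition of bleeding in three steps.

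- Step 1 extracts entries whose ICD-10 name or disease name contains the Japanese term for bleeding or haematoma.
- Step 2 goes back to the names that Step 1 left out: "To select disease names considered to be relevant to side effect of OAC individually".
- Step 3 prunes what Step 1 caught: "To exclude disease names which are not considered to be relevant to side effect of OAC".

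The table that follows prints ICD-10 codes and titles without disease-name limits. I213 appears there as "Acute transmural myocardial infarction of unspecified site".

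SAP 10.3.5 has a second table, with a column headed Subgroups. Its Bleeding history block repeats most of the codes and adds name limits to many of them. For I213 the limit is "Include only Atrial thrombus as current complication following acute myocardial infarction".

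Two parts of the analysis need a bleeding definition. The propensity-score model in SAP 7.1.2.1 includes "bleeding diagnosis in baseline" as one of 26 listed covariates. SAP 5.2.1 states: "Primary safety endpoint is incidence of major bleeding, which is defined as any bleeding requiring hospitalization". Neither section names a code list.

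**The concern.** A thrombus and a bleed are opposite kinds of event in a comparison of anticoagulants, where thromboembolic events are judged under effectiveness and bleeds under safety. A bleeding list that admits a thrombus or an infarction mixes the two.

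If the list feeds the baseline covariate, one binary variable would combine two different reasons for choosing a drug. If it feeds the outcome, a hospital admission that was not for bleeding would count as major bleeding.

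Many codes in the 10.3.4 table have non-bleeding titles, and the natural repair is to apply the 10.3.5 name limits to the outcome as well. For most rows that works. For I213 it replaces an infarction with a clot, so this row needs its own correction.

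**Working it through.** **Check of the entry against the SAP's procedure**

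| Step in 10.3.4 | I213 as titled in 10.3.4 (infarction) | I213 as limited in 10.3.5 (atrial thrombus) |
|---|---|---|
| 1: contains a bleeding or haematoma term | No, as printed in English | No, as printed in English |
| 2: added individually as relevant to an OAC side effect | Not a bleeding side effect | Not a bleeding side effect |
| 3: pruning of Step 1 names | Not reached, since Step 1 did not catch it | Not reached, for the same reason |

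The only route in is Step 2, and Step 2 does not justify either name.

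**Comparison with other rows.** Nearly every other complete include-only note in the Bleeding history block names a haemorrhage, haematoma or other bleed. The haemorrhoid entry at K649 is an exception in its English wording. The next code after I213 in both tables is I230, titled in 10.3.4 "Haemopericardium as current complication following acute myocardial infarction". That is a true bleed, and its title shares most of its wording with the I213 note.

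**Comparison with the infarction list.** The myocardial infarction list in SAP 10.3.1, so far as it can be read, shows I210, I211, I212 and I214 but not I213. On that reading the code is counted under bleeding and not under infarction.

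**What each list would do if applied as printed**

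- 10.3.5: an atrial thrombus record counts as bleeding.
- 10.3.4: any I213 infarction record counts as bleeding.

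**Size**

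Inputs from SAP 4.5: warfarin major-bleeding rate 2.5% per year, i.e. 25 per 1,000 person-years; hazard ratio 0.59; 113 events; 6,141 patients.

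The plan's own figures reproduce. The Schoenfeld formula with a hazard ratio of 0.59, two-sided alpha of 0.05 and 80% power gives 113 events. The mean of 2.5% and 1.18% is 1.84%, and 113 / 0.0184 = 6,141.

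The documents give no frequency for I213. Assume c non-bleed admissions per 1,000 person-years, equal in both arms. Then

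observed HR = (0.59 × 25 + c) / (25 + c) = (14.75 + c) / (25 + c)

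| c (assumed) | Calculation | Observed HR |
|---|---|---|
| 0.1 | 14.85 / 25.1 | 0.592 |
| 0.5 | 15.25 / 25.5 | 0.598 |
| 1 | 15.75 / 26 | 0.606 |

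At c = 0.5, which is 2% of the warfarin rate, power at 113 events falls from 80% to 78.0%.

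**The case against.** The strongest reply is that the 10.3.4 procedure selects disease names, while its table prints parent ICD titles. Pleural effusion (J90), urticaria (L508) and ascites (R18) also appear there, and 10.3.5 limits each of them to a haemorrhagic form. So an infarction title does not prove that infarctions are extracted, and a haemorrhagic disease name under I213 would be compatible with the procedure. The similarity to the I230 title makes a translation or transcription slip plausible. This stands: the documents cannot show which disease name the extraction used. It does not clear the text, because the one name limit that is printed for I213 is a clot.

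A reader might also infer more than the documents support:

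- *That a clot is scored as prior bleeding in the propensity score.* SAP 7.1.2.1 names no code list, and the 10.3.5 table is headed Subgroups, so the link is conditional.
- *That the weights would carry the wrong direction of risk.* The propensity score models treatment choice and its coefficients are estimated from the data. It imposes no direction of outcome risk. A few mislabelled records blur one covariate out of 26.
- *That a failure of stroke prevention would be scored as a safety event.* Atrial thrombus does not appear in the stroke or systemic embolism code lists (10.3.1, 10.3.3), so it is not an effectiveness event in this study.
- *That the entry contradicts Step 3.* Step 3 applies only to names caught by Step 1. The inconsistency is with Step 2.

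**Conclusion.** The I213 row is wrong as printed in both lists. Whichever list is used, applying it literally counts a non-bleed as bleeding, and carrying the 10.3.5 limits over to the outcome does not repair this row.

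The effect on the results is probably very small. At the highest rate tried, 1 per 1,000 person-years (4% of the assumed warfarin bleeding rate), the hazard ratio moves by 0.016 toward 1. That range is an assumption, as is equal frequency in the two arms; if coding differed between arms, the direction could not be predicted. The documents do not establish that the propensity score or the primary safety result is materially affected, nor that the entry reflects a deliberate choice. This is a code-list correction and does not challenge the design.

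**What to change.** 1. Check the source Japanese disease name behind I213 before changing anything. Deleting first could drop a genuine bleed if the English wording is the error.
2. If the name is a haemorrhagic condition, print it as the limit for I213 in both SAP 10.3.4 and 10.3.5. If it is atrial thrombus, delete I213 from both lists.
3. State in SAP 7.1.2.1 which list and name limits define the baseline bleeding covariate, and in SAP 5.2.1 which define major bleeding.

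The cost is one row in two lists and one sentence in each of two sections. If the bleeding flags have already been derived, a count of I213 records by cohort would show whether rerunning them could matter.
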